It is anticipated that the primary endpoint in the US will be MACrO₂ PRO symptom-based clinical response at Month 3 for the Phase 3 part of the study. However, whether this time point for the primary endpoint is at Month 3 or Month 6 will depend upon the psychometric evaluation of the PRO and the results of the Phase 2 part of the study. Outside of the US, the primary endpoint will be microbiological culture conversion by Month 6.

Study assessments and procedures will be completed at the following visits for both Phase 2 and Phase 3 parts of the study:

- **Screening Visit:** Screening assessments to determine study eligibility will be performed within 8 weeks prior to randomization as shown in [Table 3](#) in [Appendix A](#). Two to 3 sputum samples will be collected during Screening and may be collected on the same day or within a 5-day window beginning with collection of the first sample. See [Section 7.5.3](#) for additional details.
- **Treatment Period:** Day 1 to EOT; the treatment period for each patient will vary, up to a maximum of 16 months, depending on the patient's sputum culture results; see details in [Section 3.1.1](#).
 - During the first 6 months of the Treatment Period, study assessments (including microbiological, clinical, safety, and PK assessments) will be performed from Day 1 (calendar day of first dose of study drug) and every 28 days (± 7 days) thereafter, up to Month 6 (Day 169 ± 7 days).
 - Patients who culture-convert based on 3 consecutive monthly negative sputum cultures for MAC by Month 6 (Day 169 ± 7 days) will continue blinded study drug for 12 months from the first month that defines sputum culture conversion up to a maximum of 16 months in total; see [Section 3.1.1](#).
 - For patients continuing blinded study drug during the Treatment Period after Month 6, safety assessments will be performed monthly, and other assessments (including microbiological and clinical assessments) will be performed every 3 months (84 days ± 7 days), up to EOT, as specified in [Table 4](#) in [Appendix A](#).

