3.1.1. Duration of Study Drug Administration and Study Participation

For the Phase 2 and Phase 3 parts of the study, the duration of study participation for each patient, not including Screening, will be up to approximately 19 months as described in [Section 3.1](#).

Each patient's duration of study participation will vary depending on the timing of microbiological sputum MAC culture conversion. To receive study drug beyond Month 6, a patient must have achieved a microbiological sputum MAC culture conversion.

All patients will receive a minimum of 6 months of blinded study drug treatment. At the Month 6 Visit, all available sputum culture results will be assessed by the Investigator to determine whether a patient is a converter or non-converter. A converter is defined as a patient who has 3 consecutive monthly MAC-negative sputum cultures at any time within the first 6 months of the study. A non-converter is a patient who does not have 3 consecutive monthly MAC-negative sputum cultures at any time within the first 6 months of the study.

Patients who are assessed as converters will continue taking blinded study drug for 12 months after the first month that defines sputum culture conversion, up to a maximum of 16 months. Patients who are assessed as non-converters will discontinue study drug at the Month 6 Visit. Patients who are discontinued from study drug at the Month 6 Visit will complete the EOT Visit at this time point, as well as the MACrO₂ and PGIS 1 week (+1 day) after their EOT Visit, and an LFU Visit 3 months (84 days \pm 14 days) after the last dose of study drug.

Because reporting of final respiratory culture and identification results may occur up to 8 weeks after specimen receipt at the regional or central microbiological laboratory, it is unlikely that the Month 5 culture results will be available at the Month 6 Visit. Patients who have negative culture results from Month 4 and no culture data available from Month 5 will be presumed to be converters and will continue blinded study drug at the Month 6 Visit. Such patients subsequently found to have positive cultures from the Month 5 and/or Month 6 visit must be discussed with the Medical Monitor for determination of continued study drug therapy beyond Month 6. Patients with *missing* sputum cultures from any visit prior to Month 6 should not be prematurely

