3.3.7 Study Drug Exposure

For each study phase, study drug exposure will be summarized in both a Month 6 analysis (all exposures from baseline through Month 6 visit) and final analysis (all exposures from baseline through EOT visit).

The following parameters will be calculated for the exposure data:

- Duration of the oral study drug treatment (days), defined as (the earliest date of Month 6 visit or early discontinuation – date of first treatment + 1) at Month 6 analysis and (date of last confirmed treatment – date of first treatment + 1) at final analysis (through EOT Visit for all patients).
- Compliance (%) for oral study drug will be calculated as $\frac{\text{actual number of tablets taken}}{\text{planned number of tablets}} \times 100$. Actual number of tablets taken = number of tablets dispensed – returned. Planned number of tablets will be calculated as a sum of all planned doses per intake for a patient.

Study drug compliance checks will be performed by study site or home health care staff by counting the number of remaining tablets in the study drug pill bottles at each study visit. The number of actual tablets taken will be calculated as number of tablets dispensed – number of tablets returned. If study drug is not returned for one or more bottles from a given study visit, the number of tablets expected and actual tablets taken for that visit will be excluded from the compliance calculation. The number of tablets expected will be calculated as the earliest date of Month 6 visit or early discontinuation – date of first dose of study drug +1, multiplied by 2 (i.e., the number of days study drug was expected to be taken x 2 tablets per day) for the Month 6 analysis, and date of last confirmed treatment – date of first dose of study drug +1, multiplied by 2 for the final analysis. Any protocol-directed interruption in study drug use due to adverse events or changes in local laboratory creatinine clearance as recorded in the clinical database will be accounted for by calculating each interruption duration (date of restart – date of last dose prior to interruption – 1)

multiplied by 2, and subtracting these from the denominator prior to calculating overall study drug compliance. Percent compliance to the study drug regimen will be summarized by treatment based on the Safety Population with descriptive statistics and with counts and percentages of patients with compliance in the following categories:

- <80%
- 80-100%
- >100%-120%
- >120%

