Additionally, an overview of AEs listing all categories described above will be provided after adjusting for total patient-years of exposure. Incidence rates will be calculated as the number of patients who experienced one or more events in each category during the specific study duration (through Month 6 or overall), divided by the sum of the number of years of exposure across all exposed subjects in each treatment arm. Total years of exposure will be based on the duration of exposure (in days) calculated for each patient as defined in Section 3.3.7, divided by 365.25 days, and rounded to the nearest tenth of a year. Additional summaries of AE categories of SAEs, AESIs, and study drug related TEAEs by SOC (or AESI category) and PT adjusted for patient-years of exposure will also be generated.

Listings will be provided for all TEAEs, SAEs, TEAEs of special interest, TEAEs leading to study drug discontinuation, and TEAEs leading to death for all patients in the Safety Population. COVID-19-associated AEs will be coded as a specific preferred term in these listings.

A listing of all deaths, including the date of death and primary cause of death, will be presented for all patients in the Safety Population.

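### SAP 3.5.1 most naturally reads as rounding each patient's exposure to 0.1 year before summing; coded that way, exposure-adjusted AE rates would typically be about 1–7% too low

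*SAP*

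**What the plan says.** In SAP 3.5.1 the numerator counts patients, not events: "Incidence rates will be calculated as the number of patients who experienced one or more events". The denominator is the arm's person-time: the count is "divided by the sum of the number of years of exposure across all exposed subjects in each treatment arm". The next sentence gives the only conversion from days to years. It opens "Total years of exposure will be based on the duration of exposure (in days) calculated for each patient as defined in Section 3.3.7", and its operative run is "calculated for each patient as defined in Section 3.3.7, divided by 365.25 days, and rounded to the nearest tenth of a year".

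The duration in days comes from SAP 3.3.7. For the Month 6 analysis it runs from first treatment to the earlier of the Month 6 visit and early discontinuation, plus one day. For the final analysis it runs to the last confirmed treatment.

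The Protocol makes many durations cluster. Section 3.1 places Month 6 at Day 169 with a window of 7 days either side, and section 3.1.1 states: "Patients who are assessed as non-converters will discontinue study drug at the Month 6 Visit". Converters continue to a maximum of 16 months.

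The same denominator feeds the exposure-adjusted overview and the breakdowns of SAEs, AESIs and drug-related TEAEs by system organ class (or AESI category) and preferred term. SAP 3.5 says that safety analyses involve no hypothesis tests.

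**The concern.** A tenth of a year is 36.5 days, which is coarse against a planned course of about 169 days. Rounding each patient is harmless when durations are widely spread, because errors up and down cancel. It is not harmless when many patients share nearly the same duration, because they all receive nearly the same error. The Month 6 stopping rule creates such a cluster, and its centre (0.463 year) rounds up. The denominator would then be too large and the rates too small, including those for anemia and, in Phase 3, pneumonitis.

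There is also a reproducibility problem. Two programmers who both follow the sentence could obtain different denominators from the same data.

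**Working it through.** The SAP states no exposure total or AE rate, so there is no figure of its own to reproduce.

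**Formulas.** Exact years = days / 365.25. Rate error = (exact exposure / rounded exposure) − 1, since the numerator is unaffected.

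**Step 1: single durations, rounded per patient.**

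| Last day | Exact years | Counted as | Rate error |
|---|---|---|---|
| 18 | 0.0493 | 0.0 | no exposure counted |
| 85 | 0.2327 | 0.2 | +16.4% |
| 162 | 0.4435 | 0.4 | +10.9% |
| 164 | 0.4490 | 0.4 | +12.3% |
| 165 | 0.4517 | 0.5 | −9.7% |
| 169 | 0.4627 | 0.5 | −7.5% |
| 176 | 0.4819 | 0.5 | −3.6% |
| 449 | 1.2293 | 1.2 | +2.4% |

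The cut between 0.4 and 0.5 is at 0.45 × 365.25 = 164.4 days, inside the Month 6 window (Days 162–176).

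**Step 2: the two orders of operation, everyone at Day 169.**

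| n | Exact sum | Arm total rounded | Error | Each patient rounded | Error |
|---|---|---|---|---|---|
| 40 | 18.508 | 18.5 | +0.04% | 20.0 | −7.5% |
| 78 | 36.090 | 36.1 | −0.03% | 39.0 | −7.5% |
| 156 | 72.181 | 72.2 | −0.03% | 78.0 | −7.5% |

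**Step 3: mixed durations, rounded per patient.** The documents do not give the mix, so these inputs are assumptions. Mean years per patient, exact and rounded:

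- Early discontinuation, uniform over Days 1–168: 0.2313 and 0.2298.
- Stop exactly on Day 169: 0.4627 and 0.5000.
- Month 6 stop spread evenly over Days 162–176: 0.4627 and (3 × 0.4 + 12 × 0.5)/15 = 0.4800.
- Converters, equal split over Days 365, 393, 421 and 449: 407/365.25 = 1.1143 and (1.0 + 1.1 + 1.2 + 1.2)/4 = 1.1250.

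With 20% early discontinuation:

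- No converters, all others on Day 169: exact 0.2 × 0.2313 + 0.8 × 0.4627 = 0.4164; rounded 0.2 × 0.2298 + 0.8 × 0.5 = 0.4460; error −6.6%.
- 30% converters, Month 6 stops spread over the window: exact 0.2 × 0.2313 + 0.3 × 1.1143 + 0.5 × 0.4627 = 0.6119; rounded 0.2 × 0.2298 + 0.3 × 1.125 + 0.5 × 0.48 = 0.6235; error −1.9%.

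Early termination shortens Phase 3 durations. SAP section 1 puts the start of Phase 3 enrollment in September 2023 and termination on 08 August 2024, at most 343 days inclusive. Assume that entry was even over those 343 days and that dosing stopped at termination (the stop date is not stated). Capping each duration at the available follow-up and averaging over 1 to 343 days, the same two mixes give 0.3183 against 0.3325 (−4.3%) and 0.3547 against 0.3581 (−1.0%).

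For comparison, a Month 6 analysis with 0–40% discontinuation and all others on Day 169 gives −7.5% to −5.6%. Month 6 stops spread over the window with no discontinuation give −3.6%. Durations uniform over Days 1–449 give about zero.

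**Step 4: between arms.** Identical duration mixes give identical errors, so the rate ratio is unchanged. Assumed differences, with Month 6 stops on Day 169, move it as follows:

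- Conversion 30% against 10%, no discontinuation: (0.6582/0.6875)/(0.5279/0.5625) = 1.020.
- Discontinuation 30% against 10% in the Month 6 analysis: 1.010.
- Discontinuation 20% and conversion 30%, against 10% and 10%: 1.025.

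**The case against.** The strongest reply is grammatical. The subject of the sentence is the total, and the per-patient phrase describes the duration in days, so rounding may apply only to the arm total. That reading is possible, and Step 2 shows that it is harmless. It is the less natural one: computing per patient, dividing by 365.25 days and rounding form a single series, and a total already in years cannot be divided by 365.25 days. If the division acts on each patient's days, the rounding most likely does too. The order nevertheless remains unstated, so it would be wrong to assert that the SAP definitely rounds before summing.

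Two further inferences are tempting and are not supported:

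- **All exposure-adjusted rates come out too low.** Some durations round down, including Days 162–164 inside the Month 6 window, and patients who stop by Day 18 add nothing to the denominator. The mixes tried mostly give a net understatement, but not by necessity.
- **The error differs between arms and distorts the ratio.** The shift of about 2% needs 30% against 10% conversion, which is the planning assumption. SAP section 1 reports that epetraborole was not superior on culture conversion in Phase 2. Non-converters in both arms stop at about the same day, so much of the error is common and cancels.

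It is also fair that these rates are descriptive, that crude counts and percentages are reported for every category, and that programming specifications sit in a separate document that may settle the order. These points limit the consequence. They do not make the sentence unambiguous.

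**Conclusion.** The point holds as a minor one. On its most natural reading, the rule rounds each patient's exposure to 0.1 year before summing. Exposure-adjusted AE rates would then typically be about 1–7% too low, with 7.5% if every patient stopped on Day 169. The 1–7% range rests on 20% early discontinuation spread evenly over Days 1–168, 0–30% conversion, Month 6 stops either all on Day 169 or spread over the window, and Phase 3 durations with or without shortening by termination. None of these is given in the documents, and other mixes could give a smaller error or reverse its sign. The between-arm ratio is affected only if the duration mix differs by arm. If only the arm total is rounded, the error is negligible. No hypothesis test or efficacy conclusion is involved.

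**What to change.** In SAP 3.5.1, delete the clause on rounding to a tenth of a year. State that unrounded exposure days are summed within each arm, the sum is divided by 365.25, and only the displayed total is rounded. Check that the programming specifications follow the same order.

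The cost is one phrase in the SAP, with no new data and no change to any other analysis. The wording is correct under either reading; if rounding the arm total was always intended, the edit simply records that.

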3.5.2 Clinical Laboratory Tests

Laboratory panels (hematology, chemistry, and urinalysis, with specific analytes for each panel listed in Protocol Appendix B) will be summarized by scheduled visit, along with changes from baseline to each scheduled post-baseline visit (Protocol Appendix A) for each test. All summary tables will be presented by treatment, for the Safety Population. Descriptive statistics will be provided for continuous variables; for categorical variables, number and percentage will be summarized. Only data from the central laboratory will be summarized. Separate tables will be presented for each laboratory panel. All clinical laboratory results will be displayed in original units as documented in SDTM.

Shift tables (number and percentage) will be provided by CTCAE 5.0 grades from baseline to the worst post-baseline assessment and will be summarized by treatment for selected laboratory tests (hemoglobin, white blood cell count, platelets, liver function tests [alanine aminotransferase, aspartate aminotransferase, and alkaline phosphatase], and serum creatinine). The worst post-baseline grade (for both directions if applicable) will be derived from all post-baseline visits including scheduled and unscheduled. Additionally, shift tables comparing shift from baseline to each scheduled post-baseline visit with respect to normal ranges (categorizations of low, normal, or high) will be presented for all laboratory parameters where normal ranges are provided.

Additional analysis of laboratory parameters (chemistry and hematology parameters will be summarized separately) will be performed in the Safety Population and will include frequencies for the following post-baseline values:

- Patients with at least a 2-grade increase in CTCAE toxicity grade from baseline in any parameter
- Patients with CTCAE toxicity grade ≥ 4 in any parameter

Analysis of patients with post-baseline aminotransferase elevations and total bilirubin by category will be performed for the following post-baseline values in the Safety Population and defined as:

- Alanine aminotransferase $>3x$, $>5x$, $>10x$ upper limit of normal (ULN)
- Aspartate aminotransferase $>3x$, $>5x$, $>10x$ ULN
- Alanine aminotransferase and/or AST $>3x$, $>5x$, $>10x$ ULN
- Alanine aminotransferase and AST $>3x$, $>5x$, $>10x$ ULN
- Total bilirubin $>2x$ ULN
- Alanine aminotransferase and/or Aspartate aminotransferase $>3x$ ULN, and total bilirubin $>2x$ ULN

A patient with elevated laboratory parameters may belong to more than one category (e.g., if a patient has an Alanine aminotransferase value = $6x$ ULN, this patient will be presented under both $>3x$ ULN and $>5x$ ULN).

Patients who meet potential Hy's Law laboratory criteria will be listed. Hy's Law laboratory criteria are defined as any elevated Alanine aminotransferase and/or Aspartate aminotransferase of $>3x$ ULN that is associated with both an alkaline phosphatase level $<2x$ ULN and an increase in total bilirubin $>2x$ ULN.

Analysis of patients with post-baseline anemia by category will be performed for post-baseline hemoglobin values in the Safety Population and defined as:

- Baseline value \geq lower limit of normal (LLN) and postbaseline value $<LLN$
- Baseline value $\geq LLN$ and postbaseline value <10.0 g/dL
- Baseline value $\geq LLN$ and postbaseline value <10.0 g/dL to 8.0 g/dL
- Baseline value $\geq LLN$ and postbaseline value <8.0 g/dL
- Baseline value ≥ 10.0 g/dL and postbaseline value <10 g/dL
- Baseline value ≥ 10.0 g/dL and postbaseline value <10.0 g/dL to 8.0 g/dL
- Baseline value ≥ 10.0 g/dL and postbaseline value <8.0 g/dL

In the End of Study Analysis for each phase, as summary of recovery in hemoglobin results at the LFU visit by treatment arm will present the number and percentage of patients with a decrease from baseline hemoglobin of ≥ 1 g/dL at any post-baseline visit while on treatment (i.e. through the EOT visit). Among this subset of patients, the number and percentage of patients with an LFU hemoglobin result meeting the criteria of both an increase of ≥ 1 g/dL from their lowest on-therapy hemoglobin value and returning to within 1 g/dL below baseline or higher will be presented, both overall and by gender. A corresponding listing of all patients with an on-treatment hemoglobin decline in of 1 g/dL from baseline and their corresponding LFU recovery status will be provided.

All laboratory data will be listed for all patients in the Safety Population, including toxicity grades, normal ranges, and clinical significance flags; values outside their normal range will be flagged as H (high, above normal) or L (low, below normal).

Line plots of mean (\pm SD) for laboratory values (hemoglobin [separate plots for males and female], mean corpuscular hemoglobin concentration, mean corpuscular hemoglobin, mean corpuscular volume, red blood cell count [separate plots for males and females], reticulocytes percent, hematocrit [separate plots for males and females], white blood cell count, platelets, creatinine clearance, and liver function tests (alanine aminotransferase, aspartate aminotransferase, and alkaline phosphatase) versus visit will also be provided by treatment group. Normal range reference lines will be included on all figures, with the exception of creatinine clearance. Boxplots of change from baseline in hemoglobin [separate plots for males and females], mean corpuscular hemoglobin concentration, mean corpuscular volume, and red blood cell count [separate plots for males and females] will be provided by treatment group.

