If the estimated CrCl decreases to <30 mL/min at any time after initiation of blinded study drug treatment, the Investigator should recheck creatinine values at the local laboratory to verify the result and administration of study drug should be temporarily discontinued if the result is verified. In such cases, testing for creatinine levels should be performed approximately every 1 to 2 weeks to determine whether study drug can be restarted. Treatment interruption should not exceed more than 6 consecutive weeks. Patients whose treatment interruption exceeds 6 weeks will be prematurely discontinued from study drug ([Section 4.4](#)) but remain in the study to undergo all scheduled EOT and LFU assessments, including safety assessments.

All clinically significant abnormal creatinine and CrCl values must be followed until repeat tests return to normal, stabilize, or are no longer clinically significant ([Section 7.9.1](#)). Once CrCl estimates improve to ≥30 mL/min, the case must be discussed with the Medical Monitor prior to restarting study drug. No dose adjustments are allowed based on renal function changes during the study.

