5.5.2.4. Study Drug Dosing in Patients With Anemia

Patients with baseline hemoglobin <10.0 g/dL or <6.2 mmol/L (Grade 2 anemia or worse, based on CTCAE [[NIH, 2017](#)]) will be excluded from the study (see Exclusion Criterion 4). Decreases in RBC parameters (including hemoglobin, RBCs, and reticulocyte counts) have been reported in subjects receiving IV or oral epetraborole. In previous Phase 1 and Phase 2 studies of IV or oral epetraborole, reticulocyte decreases were observed within the first several days of dosing, followed by a decrease in hemoglobin (see current Investigator's Brochure for details). These hematological abnormalities appear to be transient, occur gradually, and when followed over time, return to baseline values after discontinuation of epetraborole.

Anemia is predefined as an AESI ([Section 7.9.1.2](#)). If anemia occurs during the study, the Investigator should recheck hematology values at the local laboratory to verify the result, and perform a workup to determine the cause of anemia according to his/her best clinical judgment (including, but not limited to, iron deficiency [eg, check a serum iron panel], GI bleeding, menstruation, concomitant medications [eg, non-steroidal anti-inflammatory drugs, rifamycins,

oxazolidinones, clofazimine], vitamin deficiencies [eg, vitamin B₁₂, folate], and hemolysis [eg, assess haptoglobin, blood smear]). As eptetraborole has the potential to affect only erythropoiesis, and not the production of other blood cell types (eg, lymphocytes, basophils, eosinophils, neutrophils, monocytes, or platelets), anemia with concomitant decreases in white blood cells or platelets should prompt investigation of other potential causes.

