If Grade 3 anemia or worse (hemoglobin <8.0 g/dL or <4.9 mmol/L) is identified at any time after initiation of blinded study drug treatment, the Investigator should recheck hematology values at the local laboratory to verify the result and perform a workup to determine the cause of the anemia as described above. If postbaseline Grade 3 anemia or worse is considered by the Investigator to be related to blinded study drug, administration of study drug should be temporarily interrupted. Interruption should not exceed more than 6 consecutive weeks. Patients whose temporary interruption exceeds 6 weeks will be prematurely discontinued from study drug ([Section 4.4](#)) but remain in the study to undergo all scheduled EOT and LFU assessments, including safety assessments. In such cases, hemoglobin levels should be monitored approximately every 1 to 2 weeks to ensure improvement by at least 1 grade.

All clinically significant abnormal hematology values must be followed until repeat tests return to normal, stabilize, or are no longer clinically significant ([Section 7.9.1](#)). After improvement or resolution of anemia occurs, the case must be discussed with the Medical Monitor prior to restarting study drug. No dose adjustments are allowed based on hematological changes during the study.

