Clinically significant abnormal laboratory or other examination (eg, ECG) findings that are detected during the study or are present at the time of first dose of study drug and significantly worsen during the study should be reported as TEAEs, if they cannot be ascribed to a specific medical condition or are associated with a specific underlying disease (eg, isolated elevation of ALT or AST that is not associated with a clear diagnosis or specific hepatic condition). Otherwise, abnormal laboratory values should be captured collectively under a unified disease or diagnosis (ie, a single TEAE disease term), rather than separate TEAEs for each individual laboratory abnormality. Clinically significant laboratory abnormalities or other abnormal clinical findings (eg, ECG abnormalities) include, but are not limited to, events that require intervention or if an action is taken with the study drug as a result of the abnormality. Abnormal test results that are determined to be an error should not be reported as an AE. The Investigator will exercise their medical and scientific judgment in deciding whether an abnormal laboratory finding or other abnormal assessment is clinically significant.

All clinically significant abnormal laboratory values occurring during the clinical study must be followed until repeat tests return to normal, stabilize, or are no longer clinically significant. Such laboratory values will be captured as unscheduled assessments in the electronic data capture (EDC) system if they are collected outside of protocol-defined study visits (eg, after LFU).

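### Central-laboratory-only summaries can leave a worse local hemoglobin or creatinine value out of the worst-grade, anemia-category and nadir tables

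*SAP*

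**What the plan says.** SAP 3.5.2 describes the by-visit laboratory summaries and, in that paragraph, states that "Only data from the central laboratory will be summarized". It gives no exception. The next paragraph sets out CTCAE shift tables for selected tests, including hemoglobin and serum creatinine, in which the worst post-baseline grade "will be derived from all post-baseline visits including scheduled and unscheduled". The section then counts patients whose hemoglobin falls below the lower limit of normal, 10.0 g/dL and 8.0 g/dL. It also summarises recovery at Late Follow-up against the lowest on-therapy hemoglobin.

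Protocol 5.5.2.4 has two recheck instructions. For any anemia: "If anemia occurs during the study, the Investigator should recheck hematology values at the local laboratory to verify the result". For Grade 3 or worse (below 8.0 g/dL): "the Investigator should recheck hematology values at the local laboratory to verify the result and perform a workup". Protocol 5.5.2.3 does the same for creatinine clearance below 30 mL/min: "the Investigator should recheck creatinine values at the local laboratory to verify the result". For clinically significant abnormal values obtained outside planned visits, Protocol 7.9.1 says: "Such laboratory values will be captured as unscheduled assessments".

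Protocol 7.5.2, on the other hand, assigns all eligibility and safety samples to the central laboratory and does not mention the local rechecks.

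**The concern.** Anemia is a predefined adverse event of special interest, and Protocol 1.2 reports dose-dependent hemoglobin decreases. The tables meant to describe that risk are the worst-grade shift, the category rows and the on-therapy nadir. All are extreme-value outputs, so each patient's result depends on which readings are admitted.

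The protocol directs extra readings in patients with abnormal values and names the local laboratory for the verifying one. If the SAP then admits only central results, a planned and recorded reading can be excluded from the tables in which it would matter most. A patient could have study drug interrupted on a local hemoglobin below 8.0 g/dL, be counted in the adverse event table for such interruptions, and have no matching entry in the below-8.0 g/dL row.

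**Working it through.** The plan states no figure on this point, so there is nothing to reproduce. The check sets the passages side by side and follows one patient's readings through each output.

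**1. Are local values expected to exist and be recorded?** Protocol 5.5.2.3 and 5.5.2.4 direct the local rechecks. Protocol 7.9.1 has clinically significant off-visit values entered in the database. SAP 3.3.7 refers to local creatinine clearance as recorded in the clinical database, and SAP 3.3.3 uses local values as a fallback for baseline creatinine clearance. For hemoglobin, recording of local results is inferred from Protocol 7.9.1; no passage says so by name.

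**2. Does the SAP admit them?** By the wording of 3.5.2, no. The statement on worst grade settles which visits enter but not which laboratory.

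**3. Effect on worst value.** Let C be a patient's central post-baseline hemoglobin values and L the local ones. Then min(C and L together) ≤ min(C). For serum creatinine the inequality is reversed, with max. Leaving out L therefore keeps the worst value the same or makes it milder.

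**4. Effect on the 8.0 g/dL threshold.**

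| Any central value <8.0 | Any local value <8.0 | Central-only | All sources |
|---|---|---|---|
| yes | yes | counted | counted |
| yes | no | counted | counted |
| no | yes | **not counted** | counted |
| no | no | not counted | not counted |

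Only the third row changes. It can arise because Protocol 5.5.2.4 asks for a local recheck at any anemia, so a central value of 8.0 g/dL or above can prompt a local value below it. The same table applies at 10.0 g/dL. The second row shows that a local result refuting a central one does not remove the patient under a worst-ever rule. In the banded row from 8.0 to below 10.0 g/dL, the patient would move to the more severe row if each patient is counted once at the worst value; the SAP does not say.

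**5. Effect on recovery.** Let B be baseline, N the lowest on-therapy value and F the Late Follow-up value. A patient enters the subset if B − N ≥ 1 g/dL and recovers if F − N ≥ 1 g/dL and F ≥ B − 1 g/dL.

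- Patient already in the subset: a lower local N makes F − N larger, so recovery becomes easier to show. Central-only is conservative here.
- Patient who enters only through a local N: the denominator rises by 1, and the numerator rises by 1 or 0.

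The recovery percentage can therefore move in either direction.

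**6. Creatinine.** SAP 3.5.2 has no post-baseline category for creatinine clearance below 30 mL/min. The grading output affected is the serum creatinine shift. A patient can be treated as interrupted on a local creatinine clearance in the compliance calculation (SAP 3.3.7) while that shift table omits the value.

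**7. Size.** The documents give no rate of local values that are worse than all central ones, so the number of reclassified patients cannot be derived.

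**The case against.** The strongest reply is that a recheck normally follows a central result. A central hemoglobin below 8.0 g/dL already sits in the worst-grade table and the below-8.0 row, and a local value that merely confirms it changes neither. That stands, and it limits the problem to local values that are lower, or alone in crossing a threshold.

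Second, the central-only sentence is placed with the by-visit summaries, so a narrower scope may be intended. This is possible, but the paragraph also speaks of all summary tables and no narrower scope is stated.

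Third, such cases are visible elsewhere. SAP 3.5.1 tabulates anemia events of special interest by maximum severity, and interruptions for Grade 3 or worse anemia. SAP 3.5.2 lists all laboratory data with toxicity grades. This lowers the chance of a wholly missed case but does not correct the laboratory tables.

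Fourth, central-only data are a defensible choice (one assay, one set of normal ranges). Admitting local values takes an extreme over more readings in patients selected for extra testing, which itself tends to lower the minimum. That is a fair caution and the reason to show both versions.

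Two stronger inferences are not supported. A reader might infer that most hemoglobin readings during an interruption are lost. Protocol 5.5.2.4 asks for monitoring about every 1 to 2 weeks but does not name the laboratory, and those readings are taken off drug to confirm improvement, so few would set the minimum. A reader might also infer that the difference between arms is understated. The documents give no basis for how local-only worst values would divide between arms.

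**Conclusion.** The point holds within limits and is worth changing. As written, SAP 3.5.2 excludes any local hemoglobin or serum creatinine value from the worst-grade shift, and any local hemoglobin from the category rows and the nadir. For worst grade and threshold crossings the effect is nil or towards milder results; for recovery it has no fixed direction. Its size in patients is unknown, and safety analyses are descriptive (SAP 3.5), so no test is affected.

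The conclusion assumes that the central-only sentence governs the whole of SAP 3.5.2 and that local rechecks are in the database. If the sponsor intended a narrower scope, the need reduces to stating it.

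**What to change.** In SAP 3.5.2:

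- Keep central-only data for the by-visit summaries and plots.
- For hemoglobin and serum creatinine, also produce the worst-grade shift from all recorded values, central and local. For hemoglobin, do the same for the anemia categories and the nadir and recovery summary. Show each beside the central-only version.
- Harmonise units first, since the protocol gives hemoglobin thresholds in both g/dL and mmol/L, and flag the laboratory source in the listing.

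Reconcile Protocol 7.5.2 with 5.5.2.3 and 5.5.2.4 on where safety samples are analysed.

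The cost is SAP wording, programming and a few extra tables, with no new data collection. The drawback is mixed laboratories and more frequent sampling of patients with abnormal values; showing both versions makes this visible. Under SAP Section 1, a change made after Phase 3 unblinding would have to be documented in a post hoc addendum or the study report.
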